8.3.2 Outcome Assessment

8.3.2.1 Primary Endpoint

 Incidence rate of herpetic infection with detection of talimogene laherparepvec DNA among patients Herpetic infection includes oral herpes, genital herpes, herpetic whitlow or herpetic gladiatorum of the skin, ocular herpes, herpetic encephalitis, and disseminated herpetic infection.

For either swab samples or appropriate biological sample for disseminated infection, a specialty laboratory will use a quantitative polymerase chain reaction (qPCR) test that is specific for talimogene laherparepvec DNA. Results will be reported as detectable talimogene laherparepvec DNA levels. The incidence rate will be summarized for detectable DNA results during follow-up.

8.3.2.2 Secondary Endpoints

 Count of herpetic infections with detection of talimogene laherparepvec DNA among close contacts and HCPs

Herpetic infection includes oral or genital herpes, herpetic whitlow or herpetic gladiatorum of the skin, ocular herpes, herpetic encephalitis, and disseminated herpetic infection. For either swab samples or appropriate biological sample for disseminated infection, a specialty laboratory will use a qPCR test that is specific for talimogene laherparepvec DNA. Results will be reported as detectable talimogene laherparepvec DNA levels.

 Incidence rate of herpetic infection with detection of talimogene laherparepvec DNA among patients during treatment with IMLYGIC

The incidence rate will be summarized for detectable talimogene laherparepvec DNA results from the date of first IMLYGIC dose to the date of last IMLYGIC dose + 30 days. If patients receive IMLYGIC over multiple treatment phases, the treatment period is defined as the sum of time from the date of first IMLYGIC dose to 30 days after the date

Protocol Number: 20130193 Date: 12 October 2022

of last IMLYGIC dose or the day before the subsequent treatment phase, whichever comes first, in each treatment phase.

 Incidence rate of herpetic infection with detection of talimogene laherparepvec DNA among patients after discontinuation of IMLYGIC

The incidence rate will be summarized for detectable talimogene laherparepvec DNA results during the period from 31 days after the last dose of IMLYGIC through the end of follow-up. If patients receive IMLYGIC over multiple treatment phases, each post-treatment period is defined as sum of time from 31 days after date of last IMLYGIC dose in the prior treatment phase to 1 day prior to the date the first IMLYGIC dose in the subsequent treatment phase or the end of study.

 Incidence rate of herpetic infection with detection of wild-type HSV-1 among patients during treatment with IMLYGIC

For either swab samples or appropriate biological sample for suspected herpetic infection, tests that are specific for wild-type HSV-1 should be performed per local standard of care (Centers for Disease Control, 2010; Patel et al, 2010). Results will be reported as either positive or negative for HSV-1.

The incidence rate will be summarized for positive tests occurring from the date of first IMLYGIC dose to the date of last IMLYGIC dose + 30 days. If patients receive IMLYGIC over multiple treatment phases, the treatment period is defined as the sum of time from the date of first IMLYGIC dose to 30 days after the date of last IMLYGIC dose or the day before the subsequent treatment phase, whichever comes first, in each treatment phase.

 Incidence rate of herpetic infection with detection of wild-type HSV-1 among patients after discontinuation of IMLYGIC

The incidence rate will be summarized for positive tests occurring from 31 days after the last dose of IMLYGIC through the end of follow-up. If patients receive IMLYGIC over multiple treatment phases, each post-treatment period is defined as sum of time from 31 days after date of last IMLYGIC dose in the prior treatment phase to one day prior to the date of the first IMLYGIC dose in the subsequent treatment phase or the end of study.

Summary of patient characteristics

The following baseline variables will be recorded: sex, age, **race**, **ethnicity**, Eastern Cooperative Oncology Group (ECOG) performance status, and disease stage.

Treatment patterns of anticancer therapy (eg, types and sequence)

Page 23 of 62

footnote "f" in Table 1.

Product: IMLYGIC®

Protocol Number: 20130193 Date: 12 October 2022

For more detail on what types of anticancer therapies will be recorded, please refer to

• Incidence of use of antiherpetic therapy

For more detail on what types of antiherpetic therapy will be recorded, please refer to footnote "k" in Table 1.

 Incidence of adverse events and serious adverse events during treatment with IMLYGIC

Adverse events and serious adverse events (as defined in Section 11) that occur from the date of first IMLYGIC dose to the date of last IMLYGIC dose + 30 days. If patients receive IMLYGIC over multiple treatment phases, the adverse events and serious adverse events collection period is defined as the date of first IMLYGIC dose to 30 days after the date of last IMLYGIC dose or the day before the subsequent treatment phase, whichever comes first, in each treatment phase.

 Incidence of adverse events and serious adverse events related to IMLYGIC after discontinuation of IMLYGIC

Adverse events and serious adverse events (as defined in Section 11) that occur more than 31 days after the last dose of IMLYGIC and attributed to IMLYGIC by the physician.

If patients receive IMLYGIC over multiple treatment phases, the adverse events and serious adverse events collection period is defined as 31 days after date of last IMLYGIC dose in the prior treatment phase to one day prior to the date of the first IMLYGIC dose in the subsequent treatment phase or the end of study.

Overall survival

Survival is defined by the time to death from the date of the first use of IMLYGIC. Patients who are alive or lost to follow-up at the time of the analysis will be censored.

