Amgen Proprietary - Confidential

Product: IMLYGIC®

Protocol Number: 20130193
Date: 12 October 2022
Page 3 of 62

Investigator's Agreement

I have read the attached protocol entitled "A Postmarketing Prospective Cohort Study of Melanoma Patients Treated With IMLYGIC® (Talimogene Laherparepvec) in Clinical Practice to Characterize the Risk of Herpetic Infection Among Patients, Close Contacts, and Health Care Providers; and Long-term Safety in Treated Patients", dated 12 October 2022, and agree to abide by all provisions set forth therein.

I agree to ensure that the confidential information contained in this document will not be used for any purpose other than the evaluation or conduct of the clinical investigation without the prior written consent of Amgen Inc.

Signature	
Name of Investigator	Date (DD Month YYYY)
Title:	
Name of Hospital/Site:	
Address/City/State/Country:	
Phone Number:	
Email:	

Protocol Number: 20130193 Date: 12 October 2022

[figure not shown]
Page 4 of 62

Study Design Schema

Follow-up

- observation during and after IMLYGIC® treatment
- during IMLYGIC treatment, study assessments at clinic visits for IMLYGIC treatment
- after discontinuation of IMLYGIC, study assessments every 3 months (± 30 days) via phone or routine clinic visits if they fall within the 30-day window

Collection of data from the following:

^a Median duration of IMLYGIC treatment was approximately 6 months in the clinical trial setting but may differ in clinical practice.

Protocol Number: 20130193

Date: 12 October 2022 Page 5 of 62

Table 1. Schedule of Assessments

	Screening ^a	Baseline	Assessments (approximately every 2 weeks) during IMLYGIC® treatmentb	Assessments (every 3 months ± 30 days) after discontinuation of IMLYGIC ^c
General assessments and medical history				
Written informed consent	х			
Review of eligibility criteria	х			
Patient demographics ^d		x		
Patient characteristics ^e		х		
Medical and surgical history ^f		х		
History of herpetic infection ^g		Х		
Signs and symptoms of herpetic infection ^h			х	х
Results of local laboratory testing of suspicious herpetic lesions for HSV-1, per standard of care	•		At any time –	•
Treatment received				
IMLYGIC ⁱ		X	x	
Other anticancer treatment ^j		X	x	х
Antiherpetic therapy ^k		X	x	х
Assessments of Safety and Survival				
Review of adverse events and serious adverse events during IMLYGIC treatment ^{l, m}		Х	х	

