4. ABSTRACT

Study Title

A Postmarketing Prospective Cohort Study of Melanoma Patients Treated With IMLYGIC® (Talimogene Laherparepvec) in Clinical Practice to Characterize the Risk of Herpetic Infection Among Patients, Close Contacts, and Health Care Providers; and Long-term Safety in Treated Patients

Study Background and Rationale

IMLYGIC is an oncolytic viral therapy that is approved for use in certain adults with unresectable melanoma. IMLYGIC is an attenuated herpes simplex virus type 1 (HSV-1) that was derived by functional deletion of 2 genes (infected cell protein 34.5 [ICP34.5] and ICP47) and insertion of the coding sequence for human granulocyte macrophage colony-stimulating factor (GM-CSF). The viral nature of IMLYGIC presents the potential risks of primary herpetic infection by IMLYGIC during treatment and reactivation from latent state after treatment among patients, as well as the potential risks of stimulating reactivation of latent wild-type HSV-1 in patients and of secondary transmission and infection by IMLYGIC among patient's close contacts and health care providers (HCPs). Herpetic infection may present clinically as oral or genital herpes, herpetic whitlow or herpetic gladiatorum of the skin, ocular herpes, herpetic encephalitis, and disseminated herpetic infection. To characterize these potential risks, this postmarketing prospective cohort study will follow a cohort of melanoma patients during and after treatment with IMLYGIC for up to 5 years and monitor for the potential viral transmission to their close contacts and HCPs through the existing Postmarketing IMLYGIC Surveillance Program. This study is an FDA Post Marketing Requirement #1 (PMR #1) under the pharmacovigilance plan and listed as category 3 according to the European Union Risk Management Plan.

Research Question and Objectives

Primary Objective

 Estimate the incidence rate of herpetic infection with detection of talimogene laherparepvec DNA among patients for up to 5 years after the first IMLYGIC dose

Secondary Objectives

- Count the number of herpetic infections with detection of talimogene laherparepvec DNA among close contacts and HCPs.
- Estimate the incidence rate of herpetic infection with detection of talimogene laherparepvec DNA among patients during treatment with IMLYGIC.
- Estimate the incidence rate of herpetic infection with detection of talimogene laherparepvec DNA among patients after discontinuation of IMLYGIC.

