6. RATIONALE AND BACKGROUND

6.1 Diseases and Therapeutic Area

Globally, an estimated 49,100 people die of melanoma annually, and more than one-half of these deaths occur in North America and Europe (Lozano et al, 2012). The 5-year survival, which was calculated based on information from several major medical centers, ranges from 59% for stage IIIB to 5% for stage IV M1c (Balch et al, 2009).

Since 2011, the range of therapeutic options for metastatic melanoma has significantly expanded with 6 new agents approved within 2 therapeutic classes: immunotherapies (ipilimumab, pembrolizumab, nivolumab) and BRAF- or MEK-targeted therapies (vemurafenib, dabrafenib, trametinib). Treatment combinations, including ipilimumab plus nivolumab and dabrafenib plus trametinib, are also approved options.

IMLYGIC® (talimogene laherparepvec) is an intralesionally administered oncolytic immunotherapy derived from attenuated herpes simplex virus type 1 (HSV-1) by functional deletion of 2 genes (infected cell protein 34.5 [ICP34.5] and ICP47) and insertion of the coding sequence for human granulocyte macrophage colony-stimulating factor (GM-CSF). The ICP34.5 deletion allows the virus to replicate selectively in

Amgen Proprietary - Confidential

Product: IMLYGIC®

Protocol Number: 20130193 Date: 12 October 2022

Page 17 of 62

tumors, and the deletion of ICP47 leads to antigen presentation to major histocompatibility complex class I and II molecules. The latter deletion also allows the increased expression of the US11 gene that promotes virus growth in cancer cells without decreasing tumor selectivity. Finally, the presence of GM-CSF allows stimulation of cellular immune responses. IMLYGIC has received regulatory approval in the United States, European Union, and other countries for their respective indications in the treatment of unresectable melanoma.

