8.2.5 Study Follow-up

The patient's follow-up begins at enrollment and continues through the earliest date of: 5 years after the first IMLYGIC dose, death, withdrawal of consent, or loss to follow-up. Study assessments are detailed in the Table 1. During IMLYGIC treatment, the study assessments for signs and symptoms of herpetic infection, safety, and survival are to be completed at the clinic visits for IMLYGIC treatment. After discontinuation of IMLYGIC until the end of follow-up, these study assessments are to be completed every 3 months (\pm 30 days) via phone or routine clinic visits if they fall within the 30-day window. Data collected will be transcribed into an electronic case report form (eCRF).

At any time that enrolled patients, their close contacts, or their HCPs develop a suspected herpetic lesion, they should seek medical attention to evaluate and swab any suspicious lesion for talimogene laherparepvec DNA testing (per the Postmarketing IMLYGIC Surveillance Program) or wild-type HSV-1 testing (per local standard of care) (Centers for Disease Control, 2010; Patel et al, 2010). The evaluation and reporting of suspected herpetic infections will be done according to the standard of care for IMLYGIC as described in the IMLYGIC USPI and the SmPC. In addition to these materials, for this study, patients will receive an information sheet about the study to share with their close contacts and HCPs. This information sheet will describe the study and will contain the study number for use in reporting a suspected herpetic infection.

For patients enrolled in this study, informed consent will be collected upon study enrollment to link test results from the existing Postmarketing IMLYGIC Surveillance Program to the patient (see Appendix E for a sample laboratory report from Viracor). The results will be captured in the eCRF and be included in the data analysis of the study. For close contacts and HCPs, test results from the Postmarketing IMLYGIC Surveillance Program will be linked to the study only and not to any identifiable patient information, such as the name or date of birth.

Subjects who have ended IMLYGIC treatment and entered into the follow-up period may be allowed to restart treatment if the investigator chooses. In such cases, after restarted IMLYGIC treatment is ended, subjects will continue in the follow-up period as outlined in the schedule of assessments.

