8.7.2.4.2 Analysis of the Secondary Endpoints

 Count of herpetic infections with detection of talimogene laherparepvec DNA among close contacts and HCPs

Separate counts will be reported for the number of suspected herpetic infections that are detectable for talimogene laherparepvec DNA in close contacts and HCPs.

 Incidence rate of herpetic infection with detection of talimogene laherparepvec DNA among patients during treatment with IMLYGIC

The incidence rate will be calculated as the number of suspected herpetic infections that are detectable for talimogene laherparepvec DNA divided by sum of follow-up time during treatment period with IMLYGIC dose. If patients receive IMLYGIC over multiple treatment phases, the treatment period is defined as the sum of time from the date of first IMLYGIC dose to 30 days after the date of last IMLYGIC dose or the day before the subsequent treatment phase, whichever comes first, in each treatment phase in patient-years. As a measure of precision, a 95% confidence interval will be calculated around the incidence rate.

 Incidence rate of herpetic infection with detection of talimogene laherparepvec DNA among patients after discontinuation of IMLYGIC

The incidence rate will be calculated as the number of suspected herpetic infections that are detectable for talimogene laherparepvec DNA divided by sum of follow-up time after discontinuation of IMLYGIC (last date of follow-up minus the date of last IMLYGIC dose plus 31 days). If patients receive IMLYGIC over multiple treatment phases, each post-treatment period is defined as sum of time from 31 days after date of last IMLYGIC dose in the prior treatment phase to one day prior to the date of the first IMLYGIC dose in the subsequent treatment phase or the end of study in patient-years. As a measure of precision, a 95% confidence interval will be calculated around the incidence rate.

 Incidence rate of herpetic infection with detection of wild-type HSV-1 among patients during treatment with IMLYGIC

The incidence rate will be calculated as the number of suspected herpetic infections that test positive for wild-type HSV-1 divided by sum of follow-up time during treatment period with IMLYGIC (the date of last IMLYGIC dose plus 30 days minus the date of first

Protocol Number: 20130193 Date: 12 October 2022

Page 29 of 62

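### The wild-type HSV-1 rates do not use the product-specific qPCR result, and the wording on lesion testing leaves open whether every suspicious lesion gets that qPCR

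*Protocol*

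**What the plan says.** **Wild-type endpoints.** Protocol section 8.3.2.2 says that "tests that are specific for wild-type HSV-1 should be performed per local standard of care". It names no assay. The next sentence fixes the recorded result: "Results will be reported as either positive or negative for HSV-1". Table 1 collects the same item without the word wild-type: "Results of local laboratory testing of suspicious herpetic lesions for HSV-1, per standard of care". Section 8.7.2.4.2 takes as numerator the "number of suspected herpetic infections that test positive for wild-type HSV-1", on treatment and after discontinuation. Neither section makes the count depend on the product-specific qPCR.

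**The product.** The abstract states that "IMLYGIC is an attenuated herpes simplex virus type 1 (HSV-1) that was derived by functional deletion of 2 genes". Section 6.1 says the same.

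**Testing of lesions.** Section 8.2.5, like the abstract, tells patients, close contacts and health care providers to seek care so as to "swab any suspicious lesion for talimogene laherparepvec DNA testing (per the Postmarketing IMLYGIC Surveillance Program) or wild-type HSV-1 testing (per local standard of care"). The last footnote to Table 1 instead routes suspected infections to the specialised laboratory that tests for product DNA. Section 8.3.2.1 describes that laboratory's product-specific qPCR on swab or other suitable samples.

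**Primary endpoint.** Under section 8.7.2.4.1, only suspected infections with detectable product DNA enter the numerator. The denominator is all follow-up from the first dose.

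**The concern.** The study is meant to keep two risks apart: infection by the product virus, and reactivation of latent wild-type HSV-1. Section 6.2 lists them separately. A result recorded only as HSV-1 positive does not separate them when the product is derived from HSV-1. The plan has a product-specific assay but does not use it in the wild-type definition.

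Two errors could follow, in opposite directions:

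- The wild-type rates could be too high, because product-virus lesions are counted in them.
- The primary rate could be too low. A product lesion tested only locally is lost from the numerator, while its person-time is kept.

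The second matters more. The design expects fewer than two primary events, and the loss can only make the product look safer. An analysis plan can add a classification rule later, but it cannot recover a qPCR that was never run.

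**Working it through.** **1. The plan's own figures.** Inputs from section 8.5: true rate λ = 3 per 1000 patient-years, follow-up m = 535 patient-years.

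- Expected events: λm = 0.003 × 535 = 1.605.
- Chance of at least one event: 1 − exp(−1.605) = 79.9%. The plan states 80%.
- Upper bound if none is seen (one-sided 97.5% Poisson): 3.689 / 535 = 6.90 per 1000. The plan states 6.9.

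Both reproduce at 3 per 1000. (The Table 2 column header, as it reads in the text at hand, says 1 per 1000. That rate would give 41%, so the rate in the section text is used here.)

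**2. Effect of skipped qPCR on the primary endpoint.** Let f be the share of product-positive lesions that get only the local test. The protocol gives no f, so a range is shown. The chance of at least one detected event is 1 − exp(−1.605 × (1 − f)). With no event detected, the bound on the true rate is 3.689 / (535 × (1 − f)). To restore 80%, 535 / (1 − f) patient-years are needed.

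| Assumed f | Expected detected events | Chance of at least one | Zero-event bound per 1000 | Patient-years to restore 80% |
|---|---|---|---|---|
| 0% | 1.605 | 79.9% | 6.9 | 535 |
| 10% | 1.44 | 76.4% | 7.7 | 594 |
| 20% | 1.28 | 72.3% | 8.6 | 669 |
| 50% | 0.80 | 55.2% | 13.8 | 1070 |

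**3. Do product-positive suspected lesions occur?** Section 6.2 reports a phase 2 shedding study in which 4 of 37 swabs of suspected herpetic lesions carried product DNA: 10.8% (95% CI 3.0% to 25.4%, ignoring clustering within subjects). They came from 3 of 19 subjects: 15.8% (95% CI 3.4% to 39.6%). So such lesions do arise. How many of them a local HSV-1 test would call positive is not stated. Section 6.2 also reports 16 herpetic events in the phase 3 study, none tested for the product, so product involvement in them was not assessed.

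**4. The passages side by side.**

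| Place | What it implies |
|---|---|
| 8.3.2.2, assay sentence | Wild-type-specific test, assay left to local practice |
| 8.3.2.2, result sentence; Table 1 | Result is HSV-1 positive or negative |
| 8.7.2.4.2 | Positives counted as wild-type, no qPCR condition |
| Abstract; 8.2.5 | Product DNA test or wild-type test |
| Table 1 last footnote; 8.3.2.1 | Suspected lesions go to product qPCR |

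No passage requires both tests on each lesion. None in the endpoint or analysis sections says how to count a lesion positive on both, or one positive locally with no qPCR.

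**The case against.** The strongest reply is that the protocol already asks for wild-type-specific tests, and that the word or need not be exclusive. Section 8.3.2.1 says the specialty laboratory will run qPCR. Section 8.3.2.2 says wild-type tests should be done on samples from suspected infections. The Table 1 footnote even accepts office swabs so that a viable sample is obtained in time. Section 8.3.3 refers collection details to the prescribing information and a surveillance manual that are not at hand. qPCR results are linked to the patient and entered in the eCRF, so lesions with both results can be cross-classified, and the rule for doing so could sit in the analysis plan.

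Much of this stands, and it limits what can be claimed. Three stronger readings are tempting and unsupported:

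- **That local tests do read the product as wild-type.** The protocol names no local assay and gives no cross-reactivity data. The product's origin supports could, not does.
- **That lesions are known to bypass qPCR.** The passages conflict, but no skip rate is given. The 55% figure rests on an assumed share of one half.
- **That the wild-type count is inflated by some 11% to 18%.** This comes from dividing 1.605 expected product events by 15 and by 9 patients (5% and 3% of 300). The 3% to 5% in section 8.9.1 refers to people with frequent recurrences, not to infections. The division also assumes that every product lesion is tested locally and every such test reacts. It is not an estimate.

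A lesion positive on both tests is also not automatically a product infection. The phase 2 swabs with product DNA were all negative for infectivity, so moving every dual-positive out of the wild-type rate could remove true reactivations.

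The reply does not remove the core. Asking for a wild-type-specific test while recording only HSV-1 leaves the definition open, and which tests each lesion gets has to be settled in the protocol.

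**Conclusion.** The point holds in a limited form. As written, the wild-type rates may include product-virus lesions by an amount the documents do not allow anyone to estimate. The conflict over which test a lesion receives can lower the primary rate. The planned 80% chance of at least one event would fall to about 76%, 72% or 55% if 10%, 20% or 50% of product lesions had no qPCR. Those shares are assumptions. If every lesion is in fact sent for qPCR, the 80% and the 6.9 per 1000 stand, and what remains is the wild-type definition. The study is descriptive and the wild-type rates are secondary, so no test result is at risk. The documents do not show that misclassification or event loss has occurred.

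**What to change.** - Reconcile the abstract and section 8.2.5 with the Table 1 footnote and section 8.3.2.1, using and in place of or: every swabbed suspicious lesion goes to the existing product-specific qPCR, with local HSV-1 testing alongside.
- In sections 8.3.2.2 and 8.7.2.4.2, define the main wild-type event as local HSV-1 positive with product DNA not detected.
- Keep dual-positive lesions in the primary product-DNA count, report them on their own line, and add a sensitivity analysis that includes them in the wild-type rate.
- Report HSV-1 positives without a qPCR result as HSV-1, origin undetermined.

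The cost is amendment wording and one derivation rule. Swabs, laboratory service, consent to link results and eCRF capture are already in place. The change concerns how endpoints are ascertained and alters no treatment. The drawback is that some events now counted as wild-type become undetermined.
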